Enrolled participants were randomly divided into probiotics group or placebo group. Seventeen and 19 participants were respectively assigned to the placebo group and the probiotics group. The probiotics we used were in the form of 100mg L. bulgaricus powder packets, each containing 1×10^8 CFU of probiotics (TCI CO., Taipei, Taiwan). Initially (day 1), participants underwent measurements for weight, body fat, and BMI, and fasting blood

[figure not shown]
IRB/REC No. :	CMUH110-REC2-070
Page No. :	5/28

samples were collected. Subsequently, each participant received one package of either probiotic or a placebo sample, along with drinking water on the same day. From that point onward, participants self-administered one package of the sample daily for 12 weeks and the participants' sample consumption and physical conditions were tracked by the research assistants weekly. Throughout the study duration, participants maintained their regular diet and lifestyle. At the endpoint (day 84), weight, body fat, and BMI were measured, and fasting blood samples were collected again. Weight and body fat were measured with Karada Scan 216 (OMRON, Kyoto, Japan). Alanine aminotransferase (ALT), aspartate aminotransferase (AST), blood urea nitrogen (BUN), creatinine (CRE), CHOL, HDL-C, LDL-C, TG, hemoglobin A1c (HbA1c), and Glucose-Ante Cibum (Glu-AC) levels were analyzed and reported by Laboratory Medicine in Chinese Medical University Hospital (Taichung, Taiwan). Data were expressed as the mean \pm standard error of the mean (SEM). Statistical significance between groups were done by student paired t-test or Mann-Whitney test. P-values lower than 0.05 were considered statistically significant.

Data Analysis:

The statistical analysis was conducted using GraphPad's unpaired independent samples t-test, with significance set at $*P < 0.05$.

Flow Diagram of the study:

Group	Placebo		Probiotics	
	Mean	SD	Mean	SD
Age, years	41.38	12.71	41.56	10.92
Gender, male/female	7/6		12/6	
Weight, kg	78.69	15.64	80.77	15.11
Body fat, %	32.08	6.65	30.84	5.26
BMI	29.32	5.40	28.89	3.59
ALT, U/L	26.00	15.37	32.63	18.96
AST, U/L	21.45	10.62	23.36	7.44
BUN, mg/dL	13.10	2.69	13.67	2.94
CRE, mg/dL	0.80	0.14	0.83	0.15
CHOL, mg/dL	182.18	43.04	201.60	40.97
HDL-C, mg/dL	46.82	5.82	48.50	16.26
LDL-C, mg/dL	122.82	42.15	111.01	30.40
TG, mg/dL	139.62	52.18	220.94	173.92
HbA1c, %	5.80	0.83	6.17	1.07
Glu-AC, mg/dL	93.45	16.92	109.06	34.13

Table 1: Analysis of Baseline Values of the Participants

Results

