
[figure not shown]

Figure 1: Changes in Body Composition

Placebo represents the placebo control group, and Probiotics represents the probiotics experimental group. The changes in body weight (A), body fat (B), and BMI (C) before and after consumption were calculated and expressed as a percentage of the initial values. No significant differences were observed between the two groups.

[figure not shown]

Figure 2: Changes in Blood Sugar Indices

Placebo represents the placebo control group, and Probiotics represents the probiotics experimental group. The changes in fasting blood glucose (GLU-AC) before and after sample consumption (A) and changes in glycated hemoglobin (HbA1c) expressed as a percentage of the initial values (B) were calculated. No significant differences were observed

between the two groups.

[figure not shown]

Figure 3: Changes in Blood Lipids

Placebo represents the placebo control group, and Probiotics represents the probiotics experimental group. The changes in total cholesterol (CHOL) (A), triglycerides (TG) (B), high-density lipoprotein cholesterol (HDL) (C), and low-density lipoprotein cholesterol (LDL-C) (D) before and after sample consumption were calculated. No significant differences were observed between the two groups. In the probiotics group, 65% of participants showed a decrease in TG concentration, while the placebo group had a decrease rate of 18%.

[figure not shown]

Figure 4: Changes in Liver and Kidney Function

Placebo represents the placebo control group, and Probiotics represents the probiotics experimental group. The changes in liver function indicators, aspartate aminotransferase (AST) (A) and alanine aminotransferase (ALT) (B), as well as kidney function indicators, creatinine (CRE) (C) and blood urea nitrogen (BUN) (D), before and after sample consumption were calculated. No significant differences were observed between the two groups.

IRB/REC No. :	CMUH110-REC2-070
Page No. :	10/28

Table 2: Comparative Analysis of Blood Biochemical Indices Before and After the Experiment and Changes Before and After

Variables		Probiotics	Placebo	P-value ^b
		Mean \pm SEM	Mean \pm SEM	
ALT (U/L)	Pre	32.00 \pm 4.495	31.00 \pm 6.454	0.9897
	Post	28.12 \pm 4.853	37.69 \pm 7.946	0.7713
	Change	-3.882 \pm 3.461	6.692 \pm 6.747	0.5075
	P-value ^a	0.2462	0.3799	
AST (U/L)	Pre	24.31 \pm 1.886	22.38 \pm 3.054	0.3909
	Post	22.44 \pm 2.238	25.85 \pm 4.366	0.9053
	Change	-1.875 \pm 1.530	3.462 \pm 2.043	0.34

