	P-value ^a	0.0708	0.1367	
BUN (mg/dL)	Pre	13.82 \pm 0.6765	13.17 \pm 0.8242	0.9267
	Post	12.88 \pm 0.8985	12.67 \pm 0.7914	0.9694
	Change	-0.6250 \pm 0.7465	-0.5000 \pm 0.8118	>0.999
	P-value ^a	0.5256	0.6504	
CRE (mg/dL)	Pre	0.8241 \pm 0.03584	0.7962 \pm 0.0443	0.907
	Post	0.8775 \pm 0.04979	0.7915 \pm 0.04273	0.6543
	Change	0.0475 \pm 0.02713	-0.004615 \pm 0.02087	0.34
	P-value ^a	0.0535	0.8262	
CHOL (mg/dL)	Pre	200.7 \pm 10.33	186.9 \pm 11.49	0.67
	Post	204.6 \pm 12.42	186.3 \pm 10.20	0.0719
	Change	3.882 \pm 7.086	-0.6154 \pm 3.852	0.5075
	P-value ^a	0.6526	0.8535	
Glu-AC (mg/dL)	Pre	109.3 \pm 7.834	91.77 \pm 4.590	0.3871
	Post	100.7 \pm 9.383	91.69 \pm 6.466	0.5854
	Change	1.389 \pm 2.332	-0.07692 \pm 2.962	0.7803
	P-value ^a	0.6183	0.6846	
HbA1c (%)	Pre	6.124 \pm 0.2559	5.800 \pm 0.2295	0.8619
	Post	6.407 \pm 0.3149	5.931 \pm 0.3175	0.6367
	Change	0.2067 \pm 0.05893	0.1308 \pm 0.09765	0.4821
	P-value ^a	0.0029	0.2061	
HDL-C (mg/dL)	Pre	48.55 \pm 3.820	46.82 \pm 1.613	0.3643
	Post	47.38 \pm 3.125	46.43 \pm 1.798	0.4656
	Change	-0.0125 \pm 1.362	-0.3923 \pm 1.590	0.9872
	P-value ^a	0.4037	0.7227	
LDL-C (mg/dL)	Pre	113.0 \pm 7.399	122.8 \pm 12.17	0.4531
	Post	119.0 \pm 5.992	112.4 \pm 8.306	0.5874

IRB/REC No. :	CMUH110-REC2-070
Page No. :	11/28

	Change	6.012 ± 4.366	-12.04 ± 6.323	0.0946
	P-valuea	0.4586	0.0923	
TG (mg/dL)	Pre	220.9 ± 42.18	139.6 ± 14.47	0.5469
	Post	199.9 ± 40.46	177.4 ± 36.55	0.907
	Change	-21.00 ± 11.61	37.77 ± 34.12	0.0555
	P-valuea	0.1075	0.1577	

P-valuea **paired t-test (Pre and Post groups)**

P-valueb **unpaired t-test (Probiotics and Placebo groups)**

[figure not shown]

Figure 5: Changes in Lipids Carried by Serum Lipoproteins

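### The between-arm test is an unpaired t-test with no provision for unequal variances, although Table 2 implies a 6.6-fold variance difference for triglyceride change

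*Combined protocol and SAP*

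**What the plan says.** The Data Analysis paragraph of Methods and Design states "The statistical analysis was conducted using GraphPad's unpaired independent samples t-test". Footnote b to Table 2 labels the between-arm P-values "unpaired t-test (Probiotics and Placebo groups". Neither place mentions pooled or unequal variances, a variance check or a fallback.

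The end of Study Design and Intervention gives a different account: "Statistical significance between groups were done by student paired t-test or Mann-Whitney test". There the word Student is attached to a paired test, which cannot compare two independent arms. The threshold is "P-values lower than 0.05 were considered statistically significant"; sidedness is not stated. Table 2 gives a mean and SEM of change for each arm but no n.

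**The concern.** An unpaired t-test named without qualification is ordinarily read as the pooled-variance test. That test is sensitive to unequal variances when the arms differ in size. If the smaller arm has the larger variance, the pooled standard error is too small and the test rejects too often. If the larger arm has it, the reverse holds. Table 2 appears to show both patterns. Blood lipids are among the risk factors in the stated primary goal, and TG has the smallest between-arm P-value for change in the table. The distortion would therefore be greatest on the contrast nearest the threshold.

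**Working it through.** **Inputs.** The change means and SEMs are from Table 2. The numbers analysed are inferred:
- Probiotics, TG: Table 1 SD over Table 2 SEM gives (173.92/42.18)² = 17.0. The 65% decrease rate in the Figure 3 legend fits 11/17.
- Probiotics, ALT and CHOL: the means -3.882 and 3.882 are -66/17 and 66/17.
- Placebo: (52.18/14.47)² = 13.0 for TG. The change means 37.77, -0.6154 and 6.692 are 491/13, -8/13 and 87/13.
- AST: -1.875 = -30/16 and 3.462 = 45/13, so 16 v 13.

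**Formulas.** SD = SEM × √n. Variance ratio = (SEM ratio)² × (n ratio). Pooled SE = sp × √(1/n1 + 1/n2). Welch SE = √(SEM1² + SEM2²), which needs no n; n enters only through the degrees of freedom. Tests are taken as two-sided.

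**Step 1: the printed P-values for change.** I tried to reproduce them from the same summaries (17 v 13; AST 16 v 13).

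| Analyte | Printed | Pooled | Welch |
|---|---|---|---|
| TG | 0.0555 | 0.082 | 0.124 |
| CHOL | 0.5075 | 0.613 | 0.582 |
| ALT | 0.5075 | 0.147 | 0.180 |
| AST | 0.34 | 0.042 | 0.048 |
| LDL-C | 0.0946 | 0.022 | 0.028 |

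Neither version reproduces them. The printed values do coincide with asymptotic two-sample Kolmogorov-Smirnov P-values (0.0555 and 0.5075 at 17 v 13; 0.34 at 16 v 13; 0.0946 at 17 v 12). That is an inference from matching values, made without patient data.

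**Step 2: variance ratios at 17 v 13.**
- TG: SD 47.9 v 123.0 (probiotics v placebo). (34.12/11.61)² × 13/17 = 6.60; F-test P = 0.0007.
- CHOL: SD 29.2 v 13.9. (7.086/3.852)² × 17/13 = 4.43; P = 0.013.
- ALT: SD 14.3 v 24.3. (6.747/3.461)² × 13/17 = 2.91; P = 0.049.

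**Step 3: TG in full.** sp² = (16 × 47.87² + 12 × 123.02²)/28 = 7,795, so sp = 88.3. Pooled SE = 88.3 × √(1/17 + 1/13) = 32.5. Welch SE = √(11.61² + 34.12²) = 36.0, with 14.8 degrees of freedom. The difference is -21.00 - 37.77 = -58.77. Its 95% CI is -125.4 to 7.9 pooled and -135.7 to 18.1 Welch.

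**Step 4: standard errors and error rates.** Type I error is from 200,000 simulated normal trials per analyte at 17 v 13, with true SDs set to the observed ones.

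| Analyte | Pooled SE | Welch SE | Ratio | Type I, pooled | Type I, Welch |
|---|---|---|---|---|---|
| TG | 32.5 | 36.0 | 0.90 | about 8% | 5.0% |
| ALT | 7.09 | 7.58 | 0.94 | about 7% | 5.1% |
| CHOL | 8.80 | 8.07 | 1.09 | 3.6% | 5.0% |

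**Step 5: sensitivity to n.** The Figure 3 legend says "while the placebo group had a decrease rate of 18" per cent, which fits 2/11 but no count out of 13. At 16 v 13, 18 v 13 and 17 v 11 the TG variance ratio is 7.0, 6.2 and 5.6. Pooled P for TG runs from 0.068 to 0.088 and Welch P from 0.124 to 0.128.

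**The case against.** A reader might infer that the plan specifies Student's equal-variance test. It does not. The pooled form is the usual reading of an unqualified unpaired t-test, and the neighbouring sentence also offers Mann-Whitney. What the documents show is an unstated variance assumption.

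A reader might also infer that a pooled standard error made the reported TG P-value too favourable. Step 1 rules that out: 0.0555 comes from neither t-test. Nor is there a misstated error bar to point to. Table 2 prints a separate SEM for each arm, and the readable text gives no between-arm interval.

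The evidence for unequal variances is also narrow. Three of ten analytes show it; the other seven have F-test P-values of 0.12 or more. Only TG survives a Bonferroni threshold of 0.05/10 = 0.005, and the F-test is itself sensitive to non-normality. Table 2 has no rows for weight, body fat or BMI, so nothing is shown for body weight, which the hypothesis puts first. Standard errors shift by roughly 6% to 10%, and moving from pooled to Welch crosses 0.05 for no analyte.

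All of this stands, and it limits the point's size. It does not remove the gap: the named test leaves its variance assumption open, with unequal arms and a clear variance difference on TG.

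**Conclusion.** The concern holds in a limited form. The plan names an unpaired t-test with no unequal-variance provision, and for TG the trial's own summaries contradict equal variances; for CHOL and ALT the evidence is weaker. Used in pooled form, the test would be too liberal for TG and ALT and too conservative for CHOL, by the amounts in Step 4. Those error rates are conditional on normal data, true SDs equal to the observed ones, two-sided testing and the inferred n of 17 v 13.

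It does not follow that the reported results were distorted by pooling, or that the weight comparison is affected. The mismatch between the named test and the printed P-values is a separate reason to recompute Table 2, and the recomputation should use a test whose variance assumption is stated.

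**What to change.** In Data Analysis, name one between-arm test: the two-sided Welch t-test with its 95% CI, or HC3 standard errors if a regression model is used. Remove the conflicting sentence at the end of Study Design and Intervention. Print n in every cell of Table 2, then recompute its between-arm P-values and the comparisons in Figures 1-4.

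The drafting cost is a sentence and a software setting, plus the rerun. Compared with the pooled test, intervals become slightly wider for TG, ALT and LDL-C.

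There is one consequence to prepare for. Because the printed P-values are not t-test results, a true rerun would put AST (about 0.048) and LDL-C (about 0.028) below 0.05 without multiplicity adjustment. The AST difference is -1.875 - 3.462 = -5.3 U/L, lower with probiotics. The LDL-C difference is 6.012 + 12.04 = +18.1 mg/dL, higher with probiotics. The statements of no significant differences in the legends of Figures 3 and 4 would need revisiting.

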no	S_LDL_C_pct	64.221	63.76	t-test	0.993	-0.01	0.49	0.06
no	S_LDL_FC	0.059	0.056	t-test	0.941	-0.088	0.649	0.06
no	S_LDL_FC_pct	18.211	17.591	t-test	0.966	-0.05	0.88	0.06
no	S_LDL_L	0.326	0.317	t-test	0.971	-0.043	0.317	0.06
no	S_LDL_P	0	0	t-test	0.977	-0.034	0.237	0.06
no	S_LDL_PL	0.1	0.097	t-test	0.974	-0.038	0.324	0.06
no	S_LDL_PL_pct	30.746	30.719	t-test	0.999	-0.001	0.026	0.002
no	S_LDL_TG	0.016	0.017	t-test	1.063	0.088	0.325	0.06
no	S_LDL_TG_pct	5.032	5.521	t-test	1.097	0.134	0.61	0.06
no	Sphingomyelins	0.448	0.428	t-test	0.957	-0.064	0.433	0.06
no	S_VLDL_C	0.159	0.162	t-test	1.019	0.028	0.127	0.006
no	S_VLDL_CE	0.097	0.101	t-test	1.042	0.059	0.297	0.06

IRB/REC No. :	CMUH110-REC2-070
Page No. :	23/28

no	S_VLDL_CE_pct	21.678	22.506	t-test	1.038	0.054	0.325	0.06
no	S_VLDL_C_pct	35.59	36.258	t-test	1.019	0.027	0.146	0.01
no	S_VLDL_FC	0.062	0.061	t-test	0.985	-0.022	0.101	0.005
no	S_VLDL_FC_pct	13.911	13.752	t-test	0.989	-0.017	0.086	0.005
no	S_VLDL_L	0.452	0.456	t-test	1.008	0.012	0.051	0.005
no	S_VLDL_P	0	0	t-test	1.011	0.016	0.073	0.005
no	S_VLDL_PL	0.106	0.106	t-test	0.995	-0.008	0.035	0.002
no	S_VLDL_PL_pct	23.642	23.475	t-test	0.993	-0.01	0.095	0.005
no	S_VLDL_TG	0.186	0.188	t-test	1.006	0.009	0.024	0.002
no	S_VLDL_TG_pct	40.768	40.267	t-test	0.988	-0.018	0.076	0.005
no	TG_by_PG	0.592	0.63	t-test	1.064	0.089	0.267	0.06
no	Total_BCAA	0.431	0.479	t-test	1.111	0.152	0.524	0.06
no	Total_C	4.698	4.442	t-test	0.946	-0.081	0.59	0.06
no	Total_CE	3.445	3.242	t-test	0.941	-0.088	0.625	0.06
no	Total_FA	12.405	12.095	t-test	0.975	-0.037	0.175	0.027
no	Total_FC	1.253	1.2	t-test	0.958	-0.062	0.473	0.06
no	Total_L	8.87	8.54	t-test	0.963	-0.055	0.394	0.06
no	Total_P	0.018	0.017	t-test	0.948	-0.077	0.562	0.06
no	Total_PL	2.834	2.73	t-test	0.963	-0.054	0.386	0.06
no	Total_TG	1.338	1.367	t-test	1.022	0.031	0.078	0.005
no	Tyr	0.055	0.061	t-test	1.109	0.15	0.463	0.06
no	Unsaturation	1.44	1.407	t-test	0.977	-0.033	0.814	0.06
no	Val	0.245	0.263	t-test	1.073	0.101	0.39	0.06
no	VLDL_C	0.672	0.674	t-test	1.003	0.004	0.016	0.002
no	VLDL_CE	0.394	0.396	t-test	1.004	0.005	0.021	0.002
no	VLDL_FC	0.278	0.278	t-test	1.001	0.002	0.008	0.002
no	VLDL_L	2.106	2.107	t-test	1.001	0.001	0.003	0.002
no	VLDL_P	0	0	t-test	1.016	0.022	0.111	0.005
no	VLDL_PL	0.461	0.467	t-test	1.013	0.019	0.07	0.005
no	VLDL_size	38.998	39.008	t-test	1	0	0.014	0.002
no	VLDL_TG	0.973	0.967	t-test	0.994	-0.009	0.018	0.002
no	XL_HDL_C	0.059	0.057	t-test	0.968	-0.047	0.31	0.06

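### The Figure 3 triglyceride decrease rates (65% v 18%) come without counts, and 18% is impossible with the 13 placebo participants behind Table 2; this unplanned split should be corrected and not read as evidence of effect

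*Combined protocol and SAP*

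**What the plan says.** The Results, in the Figure 3 legend, first say of the lipid panels: "No significant differences were observed between the two groups". The next sentence reads: "In the probiotics group, 65% of participants showed a decrease in TG concentration, while the placebo group had a decrease rate of 18" (per cent).

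The Study Design section gives the allocation: "Seventeen and 19 participants were respectively assigned to the placebo group and the probiotics group". The sex row of Table 1, "Gender, male/female 7/6" for placebo, implies 13 placebo participants at baseline; the probiotics entry of 12/6 implies 18. Table 1 gives baseline TG (mean and SD, placebo then probiotics) as "TG, mg/dL 139.62 52.18 220.94 173.92".

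Table 2 gives TG as mean and SEM in mg/dL:

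- Probiotics: pre 220.9 (42.18), post 199.9 (40.46), change -21.00 (11.61).
- Placebo: pre 139.6 (14.47), post 177.4 (36.55), change 37.77 (34.12).
- Between-arm P for the change: 0.0555, footnoted as an unpaired t-test.

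The Methods name the between-arm test twice and differently. Data Analysis says: "The statistical analysis was conducted using GraphPad's unpaired independent samples t-test, with significance set at" 0.05. Study Design and Intervention says: "Statistical significance between groups were done by student paired t-test or Mann-Whitney test". Neither section defines a responder, a threshold or a count of participants with a decrease.

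**The concern.** This is the only lipid figure in the report's text that is singled out as favourable, and it sits directly after a statement of no difference. A reader who tests 65% against 18% will find nominal significance that the analysis of TG change does not show. An any-decrease count has no threshold, so a fall of 1 mg/dL counts the same as one of 200 mg/dL. No other laboratory variable is given a decrease rate in the text, not even LDL-C, where the mean change favoured placebo (-12.04 v +6.012 mg/dL). If the placebo percentage also does not come from the participants in Table 2, the contrast cannot be traced to the trial's own data.

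**Working it through.** **Step 1: participants behind the TG rows.** Since SEM = SD/√n, n = (SD/SEM)², with SDs from Table 1 and SEMs from Table 2.

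- Probiotics: (173.92/42.18)² = 17.00
- Placebo: (52.18/14.47)² = 13.00

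As a second check on placebo, 37.77 × 13 = 491.0. If TG was recorded in whole mg/dL, 13 is the only n from 8 to 19 that gives 37.77. Post minus pre equals the printed change in both arms (199.9 - 220.9 = -21.0; 177.4 - 139.6 = 37.8), so the three rows appear to use the same people.

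**Step 2: which fractions give the printed percentages.** All x/n with n from 5 to 19 were listed.

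- 65%: only 11/17 = 64.7%. This agrees with Table 2; nothing out of 18 or 19 fits.
- 18%: only 2/11 = 18.2% or 3/17 = 17.6%.
- With n = 13, the neighbouring values are 2/13 = 15.4% and 3/13 = 23.1%.

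The probiotics figure reproduces on the Table 2 set; the placebo figure does not. An 11-person placebo set is plausible, because some Table 1 placebo means fit n = 11 (Glu-AC 93.45 = 1028/11; AST 21.45 = 236/11). A denominator of 17 is the number randomised to placebo. In that case the probiotics arm would be using 17 of its 19 randomised, so the arms would be handled differently.

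**Step 3: how the split tests** (Fisher exact, two-sided).

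- 11/17 v 2/11: P = 0.024
- 11/17 v 3/17: P = 0.013

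For a placebo denominator of 13, P is 0.010 at 2/13, 0.033 at 3/13 and 0.14 at 4/13. The documents do not say which count is right.

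**Step 4: how the TG change tests,** at 17 v 13, two-sided. Difference = -21.00 - 37.77 = -58.77 mg/dL. The SDs of change are 11.61 × √17 = 47.9 and 34.12 × √13 = 123.0.

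- Pooled: SD = √[(16 × 47.9² + 12 × 123.0²)/28] = 88.3; SE = 88.3 × √(1/17 + 1/13) = 32.5; t = -1.81 on 28 df; P = 0.082; 95% CI -125.4 to 7.9.
- Welch: SE = √(11.61² + 34.12²) = 36.0; t = -1.63 on 14.8 df; P = 0.124; 95% CI -135.7 to 18.1.

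The printed 0.0555 matches neither. With a placebo n of 11 the values are 0.067 and 0.128. All of these exceed 0.05.

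**Step 5: baseline imbalance.** The covariance of pre and post is [Var(pre) + Var(post) - Var(change)]/2, and the slope of post on pre is covariance/Var(pre).

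- Probiotics: slope (42.18² + 40.46² - 11.61²)/(2 × 42.18²) = 0.92
- Placebo: slope (14.47² + 36.55² - 34.12²)/(2 × 14.47²) = 0.91
- Pooled within arms: 0.921

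The baseline gap is 220.94 - 139.62 = 81.32 mg/dL. Expected regression to the mean is (1 - 0.921) × 81.32, or about 6 mg/dL of the 58.8.

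The baseline-adjusted difference at day 84 is (199.94 - 177.39) - 0.921 × 81.32, or about -52.4 mg/dL. Here 199.94 = 220.94 - 21.00 and 177.39 = 139.62 + 37.77. The SE is 34.4 on 27 df, giving a 95% CI of -123.0 to 18.2 and P = 0.14.

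**The case against.** The strongest reply is that the legend makes no claim. It states non-significance first, attaches no test to the percentages, and zero is a natural dividing line for a change. The split also points the same way as the mean change (-21.00 v +37.77), so the two do not conflict. All of that stands. The fault is selective emphasis plus an untraceable figure, not a false claim of significance, and nothing shows that the cut-point was chosen from the results.

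A reader might infer that two placebo participants were left out. The documents do not establish this, because 3/17 also rounds to 18%. Figure 3 itself is not shown in the text available here, so any counts printed on it cannot be seen.

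A reader might also infer that regression to the mean produced the contrast, since probiotics started about 81 mg/dL higher. The direction is right, but Table 2's own SEMs imply only about 6 mg/dL. Those slopes come from small, skewed samples, so baseline imbalance is a secondary caution.

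The appendix is tempting too. Table 4 gives placebo "Total_TG 1.338 1.367" mmol/L at the two visits, which hardly differ, while the hospital assay rises by 37.77 mg/dL. But Table 4 states no number of participants and uses another assay, so it does not show that a few values drove the rise.

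Finally, P = 0.0555 may be a Mann-Whitney result, since the Methods also name that test. This cannot be checked from summaries, so the mismatch is with the unpaired t-test in the Table 2 footnote.

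**Conclusion.** The point holds in this form: the placebo rate of 18% cannot come from the 13 participants behind the Table 2 TG rows, its denominator is unstated, and the any-decrease split is not described in the Methods. Either fraction that fits (2/11 or 3/17) leaves the placebo denominator at odds with Table 2.

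The split gives a stronger impression (Fisher P = 0.024 or 0.013) than the difference in mean change (P = 0.082 pooled, 0.124 Welch, 0.0555 as printed) or the baseline-adjusted difference (P = 0.14). It does not follow that a correct count would lose nominal significance: at 2/13 or 3/13 it would stay below 0.05, and at 4/13 it would not.

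The n of 13 from SD and SEM assumes that Tables 1 and 2 describe the same baseline TG values, which the matching means support. The whole-number check assumes integer TG. The t-tests assume two-sided testing, since sidedness is not stated. The adjusted estimate assumes a common slope and residual variance on the raw scale. With SDs of change of 48 and 123, and skewed TG, it is approximate.

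**What to change.** Correct the placebo figure by printing x/n by arm for everyone with both TG values (17 and 13 on the Table 2 evidence), reconciled to Table 2 and labelled post hoc; or delete the sentence. In either case, do not present the split as evidence of effect.

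Lead with the between-arm difference in TG at day 84 adjusted for baseline TG, with its 95% CI, in the same participants as Table 2. A log scale is reasonable given the skew. State which test produced 0.0555, and make the two descriptions of the between-arm test in the Methods agree.

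The cost is one reanalysis of data already collected and one rewritten sentence. The claim becomes less favourable.

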Lactobacillus is a type of lactic acid bacterium commonly found in the human gastrointestinal tract and in fermented dairy products such as cheese, yogurt, and kefir [14]. The isolation of specific probiotic strains for targeted application is a strategy for improving the efficacy of probiotic supplements. Some species of *Lactobacillus*, such as *L. gasseri* and *L. rhamnosus*, have been evaluated for inducing weight loss [15]. *Lactobacillus delbrueckii* ssp. *bulgaricus* (*L. bulgaricus*) is one of the most common lactobacilli starters used in the manufacture of a large variety of fermented milk products. *L. bulgaricus* is reported to exhibit an outstanding inhibitory effect on pancreatic lipase activity in vitro and effectively managed the fat and weight accumulation and reversed the increased blood lipid, sugar, and insulin levels caused by a high-fat diet in mice [16]. Our hypothesis posits that *L. bulgaricus* can contribute to the reduction of body weight and alleviate health risk factors associated with obesity in overweight individuals. Thus, the objective of this study was to examine the effectiveness of daily *L. bulgaricus* supplementation in weight management among overweight participants. The primary goal is to evaluate its impact on lowering body weight and addressing health risk factors related to obesity, including blood lipid levels, sugar regulation, and insulin levels.

IRB/REC No. :	CMUH110-REC2-070
Page No. :	4/28

Methods and Design

Participants:

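### Table 2: the probiotics fasting-glucose row contradicts itself (Pre and Post imply -8.6 mg/dL, Change prints +1.389), and the Post mean is the likelier error

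*Combined protocol and SAP*

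**What the plan says.** The Background section includes glucose in the primary goal, which covers "addressing health risk factors related to obesity, including blood lipid levels, sugar regulation, and insulin levels". Results, Figure 2 reports the before-to-after change in fasting glucose (panel A) and the percentage change in HbA1c (panel B), and states that the arms did not differ significantly.

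Table 2 gives the Glu-AC numbers, with probiotics first, placebo second and the between-arm P-value last:

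- Pre: "109.3 \pm 7.834 91.77 \pm 4.590 0.3871"
- Post: "Post 100.7 \pm 9.383 91.69 \pm 6.466 0.5854"
- Change: "Change 1.389 \pm 2.332 -0.07692 \pm 2.962 0.7803"

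The within-arm P-values are 0.6183 (probiotics) and 0.6846 (placebo). The table footnote names a paired t-test within arms and an unpaired t-test between arms. Study Design and Intervention also names the Mann-Whitney test. Table 2 prints no n for any row. On numbers, the same section says: "Seventeen and 19 participants were respectively assigned to the placebo group and the probiotics group". The gender counts in Table 1 give 12 + 6 = 18 probiotics and 7 + 6 = 13 placebo participants.

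**The concern.** On one set of participants, the mean change equals the Post mean minus the Pre mean. The probiotics glucose row breaks this identity in size and in direction. One pair of figures says that fasting glucose fell on the probiotic; the Change figure says that it rose slightly.

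This outcome belongs to the stated primary goal. Someone who extracts the Pre and Post means, for example for a meta-analysis, would record a fall of 8.6/109.3 = 7.9%. Someone who extracts the Change row would record a rise of 1.389 mg/dL. The table does not show which is right.

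**Working it through.** **1. The identity across Table 2.** Post - Pre was set against the printed Change for ten analytes in two arms (20 cells). The placebo glucose cell reproduces: 91.69 - 91.77 = -0.08 against -0.07692. In the probiotics arm, ALT, AST, CHOL, LDL-C and TG reproduce to rounding. These cells do not:

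| Cell | Post - Pre | Printed Change | Gap as a multiple of the Change SEM |
|---|---|---|---|
| Probiotics Glu-AC | -8.6 | +1.389 | 9.99/2.332 = 4.3 |
| Probiotics HbA1c | 0.283 | 0.2067 | 0.0763/0.05893 = 1.3 |
| Probiotics HDL-C | -1.17 | -0.0125 | 1.1575/1.362 = 0.85 |
| Probiotics BUN | -0.94 | -0.6250 | 0.315/0.7465 = 0.42 |
| Probiotics CRE | 0.0534 | 0.0475 | 0.0059/0.02713 = 0.22 |
| Placebo LDL-C | -10.4 | -12.04 | 1.64/6.323 = 0.26 |

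Only glucose changes sign. Rounding of the two means allows -8.7 to -8.5, so rounding is not the cause. The other gaps look like Pre, Post and Change computed on different participants.

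**2. Can missing pairs explain the glucose cell?** Assume that glucose is recorded in whole mg/dL. The placebo change supports this: -0.07692 = -1/13. With at most 19 pairs, the only whole-number total that gives 1.389 is 25/18 = 1.3889. So there are 18 pairs, the Table 1 count, and with 19 randomised at most one unpaired value is possible. Three cases remain:

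- *18 Pre, 18 Post.* The three figures must add up. They do so only if Post = 109.3 + 1.389 = 110.7 or Change = -8.6.
- *19 Pre, 18 Post.* The unpaired Pre value is 19 × 109.3 - (18 × 100.7 - 25) = about 289 mg/dL. This implies a sum of squares of at least (289.1 - 109.3)² × 19/18 = about 34,100. The printed Pre SEM allows 18 × 19 × 7.834² = 20,989. Not possible.
- *18 Pre, 19 Post.* The unpaired Post value is 19 × 100.7 - (18 × 109.3 + 25) = about -79 mg/dL. Not possible.

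**3. Which figure do the printed tests fit?** A change of +1.389 with SEM 2.332 gives t = 0.60, and with 17 degrees of freedom P = 0.56 (printed 0.6183). The between-arm difference is 1.389 + 0.077 = 1.47, and with n = 18 and 13 the unpaired t-test gives P = 0.70 (printed 0.7803). Neither is exact, but both fit a change near zero.

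**4. Effect on the Day-84 comparison**, with the printed Post SEMs and n = 18 and 13 assumed:

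- Post 100.7: 100.7 - 91.69 = +9.0 mg/dL, P = 0.44 (Welch) to 0.47 (pooled).
- Post 110.7: 110.7 - 91.69 = +19.0 mg/dL, P = 0.11 (Welch) to 0.14 (pooled).

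**The case against.** **Whole-number values are an assumption.** If glucose is not in whole mg/dL and at least two pairs are missing, the figures could coexist. With 19 Pre values and 17 pairs, for example, the two excluded baselines would average about 194 mg/dL, which the Pre SEM allows. This stands, so the claim that a figure is wrong is conditional. Even then, Pre and Post would describe different people with no n printed, and the same correction would be needed.

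**A reader might infer a hidden benefit**, namely that a change of -8.6 would make the unpaired t-test significant in the probiotic's favour. The documents do not support this, for three reasons:

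- The test would join the -8.6 mean to the SEM of the very Change figure taken to be wrong. If that figure is wrong, its SEM is unknown.
- The printed P-values of 0.6183 and 0.7803 would also have to be wrong.
- Table 2's P-values do not follow a plain t-test on its summary figures. For AST change (n = 16 and 13, inferred from the means) the t-test gives about 0.04, where the table prints 0.34. For LDL-C change (n = 17 and 11 to 13) it gives about 0.02, where the table prints 0.0946. A recalculated t-test therefore does not show what the table would have reported.

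**The Post P-value could seem to favour 100.7.** The printed 0.5854 lies nearer to the 0.44-0.47 obtained with 100.7 than to the 0.11-0.14 obtained with 110.7. But the undisputed Pre row prints 0.3871 where the pooled t-test gives 0.09, so this P-value cannot decide between them.

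**Sugar regulation does not rest on this cell alone.** HbA1c is also reported. It rose within the probiotics arm (change 0.2067, P = 0.0029) with no significant difference between arms (P = 0.4821), and gives no support to a glucose benefit.

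**It may be one digit.** 100.7 and 110.7 differ by one character, and the text reviewed here was extracted from a PDF, so a misread digit must be ruled out on the original page.

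**Conclusion.** The probiotics Glu-AC row is inconsistent as it stands: -8.6 from Pre and Post against +1.389 in the Change row, a gap of 10 mg/dL with opposite signs. If glucose values are whole numbers, at least one printed figure is wrong.

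The evidence leans towards the Post mean. A value of 110.7 restores the identity exactly, and the P-values for change and the Figure 2 text agree with +1.389. On that reading the conclusion of no significant difference probably stands, and what changes is the Day-84 arm difference, from +9.0 to about +19.0 mg/dL (still not significant by t-test, assuming n of about 18 and 13). The documents cannot prove this; the source data must confirm it.

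The smaller gaps in five other cells point to a wider reporting fault: Table 2 appears to mix denominators without saying so.

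**What to change.** 1. Check the Glu-AC rows on the original page.
2. Recompute Pre, Post and Change for probiotics Glu-AC from the participant-level laboratory file, on the same paired participants, and print n.
3. Correct whichever figure is wrong: Post becomes 110.7 if +1.389 is confirmed, or Change becomes about -8.6, with its own recomputed SEM, if 100.7 is confirmed.
4. Rerun the Post and Change tests for that row, name the test used, and make Figure 2A and its text follow.
5. Print n for the other rows that do not add up: probiotics BUN, CRE, HbA1c and HDL-C, and placebo LDL-C.

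The cost is a recheck of one laboratory variable in at most 19 participants, one corrected row, possibly one figure, and some added counts. No new data are needed. If Post proves to be the wrong figure, the apparent 8.6 mg/dL fall disappears from the table.
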